6 HYPOTHESES AND OBJECTIVES OF THE STUDY

6.1 Working hypothesis

The ophthalmic solution PRO-157 is so safe and effective in any of its different posologies when demonstrating non-inferiority when compared against Moxifloxacin and Gatifloxacin in the treatment of bacterial conjunctivitis.

Ho: The ophthalmic solution PRO-157 is not as safe and effective in any of its different dosages when it shows no inferiority when compared to Moxifloxacin and Gatifloxacin in the treatment of conjunctivitis.

Ha: The ophthalmic solution PRO-157 is so safe and effective in some of its different posologies when demonstrating non-inferiority when compared against Moxifloxacin and Gatifloxacin in the treatment of conjunctivitis.

6.2 Objectives

General purpose:

To evaluate the safety and efficacy of the ophthalmic solution PRO-157 in three different posologies versus Moxifloxacin and versus Gatifloxacin in patients with bacterial conjunctivitis.

Specific objectives:

To determine the safety of the PRO-157 solution in three different posologies versus Moxifloxacin and versus Gatifloxacin in patients with bacterial conjunctivitis by the incidence of adverse events and visual capacity.

To evaluate the efficacy of the ophthalmic solution PRO-157 in three different posologies versus Moxifloxacin and versus Gatifloxacin in patients with bacterial conjunctivitis through conjunctival cul-de-sac culture and the clinical evaluation of some ocular signs and symptoms such as: burning, lacrimation, Foreign body sensation, pruritus, photophobia, conjunctival hyperemia, chemosis, secretion, palpebral edema, membranes and / or pseudomembranes, scales and epitheliopathy.

7 STUDY DESIGN

7.1 Point or limit points

Criteria for the evaluation.

Efficacy measurements:

Main efficacy criterion

Efficacy will be determined by taking cultures of the lower conjunctival cul-de-sac background quantifying (colony-forming units) and identifying genus and basal and final microbial species.

It will be determined as effective if there is a reduction in the number or species of bacterial flora comparing the basal culture against the end between the five different groups of patients and / or if there is a reduction or absence of the following specific signs and symptoms: burning, tearing, Foreign body sensation, pruritus, photophobia, conjunctival hyperemia, chemosis, palpebral edema and secretion, membranes and / or pseudomembranes when comparing the study medication versus Moxifloxacin and versus Gatifloxacin from baseline to final visit.

Efficiency parameters

- The effectiveness of the drug will be evaluated by means of:

1. Clinical referral

2. Microbiological remission

Clinical remission will be evaluated by means of the signs and symptoms that the patient presents at the beginning and at the end of the study.

Variable	Operationalization	Measurement scale	Value
Secretion	Dependent Qualitative ordinal	Absent Present	Must be recorded as absent in 95% of the subjects evaluated
Conjunctival hyperemia	Dependent Qualitative ordinal	Absent Mild Moderate Severe	You must comply with the following: • Absent \geq 95.0% • Mild \leq 5.0% • Moderate \leq 2.5% Severe \leq 1.0%
Chemosis	Dependent Qualitative ordinal	Absent Present	Must be recorded as absent in 95% of the subjects evaluated
Eyelid edema	Dependent Qualitative ordinal	Absent Present	Must be recorded as absent in 95% of the subjects evaluated
Corneal epithelial defects	Dependent Qualitative ordinal	Affected area, percentage	Percentage of affected area less than 95%

The microbiological remission will be evaluated by means of the culture taken from the conjunctival sac fundus.

Variable	Operationalization	Measurement scale	Value
Culture	Dependent Discrete quantitative	UFC * / ml Eradication Reduction Proliferation	Must be recorded as absent in 95% of the subjects evaluated

* Colony forming units

The drugs under study will be considered effective if the patient has any of the following:

1. Clinical remission + Microbiological remission.
2. Clinical referral.
3. Microbiological remission.

Security measurements:

Adverse events and visual capacity.

Evaluation parameters

• The safety of the use of PRO-157 will be evaluated in the visits indicated in the schedule, through the following parameters:

1. Visual capacity
2. Eye surface
3. Exploration of the previous segment
4. Exploration of the posterior segment
5. Burning
6. Foreign body sensation
7. Lachrymation
8. Conjunctival hyperemia
9. Itching
10. Photophobia
11. Chemosis
12. Tear discharge
13. Eyelid edema
14. Membranes / pseudomembranes
15. Scales
16. Corneal epithelial defects
17. Adverse events

It will be considered that the drug under evaluation is safe for use in humans if there are no changes in the parameters indicated in more than 5% of the subjects, in both eyes, if the

patient goes to all the visits of the study and complies with adherence to treatment $\geq 80\%$ during the time of evaluation of the study.

Variable	Operationalization	Measurement scale	Value
Visual ability	Independent Discrete quantitative	Points logMAR 0-1 0 = Snellen 20/20	Do not present change in 1 line in the Snellen letter or in 1 logarithmic point (log MAR)
Ocular surface	Dependent Qualitative ordinal	Absent Present	Abnormalities in any area of the ocular Surface
Exploration of the previous segment	Dependent Qualitative ordinal	Normal Abnormal	Abnormalities in any of the structures included: cornea, iris, pupil, irido-corneal and crystalline angle.
Exploration of the posterior segment	Dependent Qualitative ordinal	Normal Abnormal	Abnormalities in any of the structures included: vitreous, retina, macula and the optic nerve
burning	Dependent Qualitative ordinal	Absent Present	Must be recorded as absent in 95% of the subjects evaluated
strange body sensation	Dependent Qualitative ordinal	Absent Present	Must be recorded as absent in 95% of the subjects evaluated
tearing	Dependent Qualitative ordinal	Absent Present	Must be recorded as absent in 95% of the subjects evaluated

Secretion	Dependent Qualitative ordinal	Absent Present	Must be recorded as absent in 95% of the subjects evaluated
Conjunctival hyperemia	Dependent Qualitative ordinal	Absent Mild Moderate Severe	You must comply with the following: Absent ≥ 95.0% Mild ≤ 5.0% Moderate ≤ 2.5% Severe ≤ 1.0%
Photophobia	Dependent Qualitative ordinal	Absent Mild Moderate Severe	You must comply with the following: Absent ≥ 95.0% Mild ≤ 5.0% Moderate ≤ 2.5% Severe ≤ 1.0%
Chemosis	Dependent Qualitative ordinal	Absent Present	Must be recorded as absent in 95% of the subjects evaluated
Eyelid edema	Dependent Qualitative ordinal	Absent Present	Must be recorded as absent in 95% of the subjects evaluated
Membranas Pseudomembranes	Dependent Qualitative ordinal	Absent Present	Must be recorded as absent in 95% of the subjects evaluated
Scales	Dependent Qualitative ordinal	Absent Present	Must be recorded as absent in 95% of the subjects evaluated

Epithelial defects corneal	Dependent Qualitative ordinal	Affected area, percentage	Percentage of the affected area 95%
Adverse events	Dependent Qualitative ordinal	serious Not Serious	Must be recorded as absent in 95% of the subjects evaluated

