Ha: The ophthalmic solution PRO-157 is so safe and effective in some of its different posologies when demonstrating non-inferiority when compared against Moxifloxacin and Gatifloxacin in the treatment of conjunctivitis	

Sponsor's name: Laboratorios Sophia, S.A. of C.V.

Finished Product Name: NA

Active Ingredient Name: Pazufloxacin

Methodology

Multicentric double randomized study masked.

Number of participants: 300 eyes, 60 eyes per treatment group

Diagnosis and main criteria for inclusion

Patients with bacterial conjunctivitis (signs and / or symptoms and / or culture)

Subjects aged 0 years to 99 years.

Study medication:

Pazufloxacin

- **Treatment duration:**
- - **Recruitment period: 4 months**
- - **Period of treatment: 7 days**
- - **Period of follow-up: 15 days**

Criteria for evaluation:

Efficacy measurements:

Main efficacy criterion

It will be determined as effective if there is a reduction in the number or species of bacterial flora comparing the basal culture against the final between the five different groups of patients and / or if there is a reduction or absence of the infection with the clinical evaluation through signs and symptoms such as: burning, tearing, foreign body sensation, pruritus,

photophobia, conjunctival hyperemia, chemosis, secretion, palpebral edema, membranes and / or pseudomembranes, palpebral scales and epitheliopathy

Security measurements:

Visual ability

Adverse events

INDICE

1. Summary of the study	2
2. Glossary and definitions	6
3. Administrative structure of the study	7
3.1 Parties not sponsored.	7
3.2 Sponsored parties	8
4. Background information	8
4.1 Justification	9
4.2 Non-clinical pharmacology	11
5. Clinical Studies	17
6. Hypothesis and Objectives	17
6.1 Work hypothesis	17
6.2 Objectives.	19
7. Point or points limit	19
8. Study plan	25
9. Measures to minimize deviations	29
10. Products administered	30
11. Description of the packaging	31
12. Management of the study medication	31
13. Closure of the center	33
13.1 Premature discontinuation of study	31
13.2 Center closure	31
14. Source data	33
15. Selection and withdrawal of subject of study	33
15.1 Inclusion criteria	33
15.2 Exclusion criteria	34
15.3 Criteria for patient withdrawal	36
16. Treatment of the study subjects	37
16.1 Managed treatments	37
16.2 Delivery of treatment	37
16.3 Previous and concomitant treatments	37
16.4 Treatments authorized during the study	39
16.5 Drug compliance	39
17. Methods and times of measurements	39

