4 INFORMATION ABOUT BACKGROUND

4.1 INTRODUCTION

Conjunctivitis (partial or total inflammation of the conjunctiva) caused by an external pathogen can be divided into bacterial and viral, however we must not forget that if we take into account its etiology we can name by fungal, allergic, autoimmune and by physical means (heat burns, friction, chemical).

In the following document, we will concentrate on exposing the epidemiological and clinical panorama of conjunctivitis caused by pathogens (bacteria and viruses) and the suffering related to the mass.

Currently about 6 million cases are registered per year in the general consultation (1% of the total annual consultations), this does not mean that all cases will be sent to the ophthalmologist, however as a reason for consultation 70% of the subjects come first with a family doctor and 35% refer to ophthalmologists because it is a case that does not remit with symptomatic or because the severity warrants it.

The cost of treating conjunctivitis according to data collected in the American union represents more than 377 million dollars a year.

Viral conjunctivitis:

Viral conjunctivitis represents an average of 80% of reported cases, it is estimated that 50% of these will be misdiagnosed as bacterial, this when compared to positive cultures.

65-90% of cases are caused by adenoviruses found in any of its two pathogenic entities, either in the form of epidemic keratoconjunctivitis or pharyngo-conjunctival fever. Clinically both are characterized by local inflammatory reactions, hyaline secretion, chemosis, photophobia, hyperemia, corneal deposits and lymphadenopathy.

The adenovirus is highly contagious and an estimated 10 to 50% chance of spread. 46% of the cultures in the hands of patients diagnosed with keratoconjunctivitis are positive, so their spread is verified mainly by contact and fomites.

Its incubation period ranges from 5 to 12 days and its transmission period of 10-14 days.

Its treatment consists of treating the symptoms with eye lubricants, NSAIDs, eye antihistamines, cold compresses, etc. Prophylaxis with antibiotics is not indicated since its benefit has not been proven, more if complications and delay in diagnosis of other entities are reported.

Bacterial conjunctivitis:

Its incidence is estimated at 135 per 10,000 inhabitants. The main routes of infection are by contact, although the proliferation of normal flora can occur as sole etiology or concomitantly.

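### The labelled main efficacy criterion is an and/or composite that the rest of section 7.1 contradicts, so the non-inferiority comparison has no single scorable primary endpoint.

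*Combined protocol and SAP*

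**What the plan says.** Section 7.1, under Main efficacy criterion, opens with culture: "Efficacy will be determined by taking cultures of the lower conjunctival cul-de-sac background". The next paragraph counts treatment as effective if there is a "reduction in the number or species of bacterial flora comparing the basal culture against the end", and/or if any of ten listed signs and symptoms is reduced or absent. The synopsis gives the same and/or rule under the same heading.

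Under Efficiency parameters, section 7.1 names clinical and microbiological remission and tabulates five signs plus culture. Culture, secretion, chemosis and eyelid edema carry the entry "Must be recorded as absent in 95% of the subjects evaluated". Hyperemia has a graded distribution across subjects, and corneal defects pass if the affected area is below 95%. The section closes with a patient-level rule: "The drugs under study will be considered effective if the patient has any of the following". Three outcomes follow, namely both remissions, clinical alone or microbiological alone.

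The surrounding text is not uniform either:
- **Signs.** There are ten in the and/or rule, five in the tables and twelve in the synopsis, whose list ends with "membranes and / or pseudomembranes, palpebral scales and epitheliopathy". Section 6.2 also lists twelve and evaluates efficacy "through conjunctival cul-de-sac culture and the clinical evaluation of some ocular signs and symptoms".
- **Unit.** The closing rule uses the patient and the tables use subjects. The synopsis and section 8 use eyes, and section 23 uses both patients and eyes.
- **Hypothesis.** Section 6.1 calls the product safe and effective "when demonstrating non-inferiority when compared against Moxifloxacin and Gatifloxacin in the treatment of bacterial conjunctivitis". No margin is stated.
- **Population.** Section 15.1 accepts a diagnosis on signs, symptoms or culture. Section 18.2 starts treatment whatever the culture shows. Neither the ITT nor the PP definition requires a positive culture.

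**The concern.** A primary endpoint must let two analysts with the same data reach the same verdict. Here a patient with fewer colonies, persistent growth and persistent signs succeeds under the and/or rule but has neither remission in any ordinary sense. If the text does not say which statement governs, the choice can be made after the data are seen.

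The lenient rules also matter for direction. The protocol says these infections generally resolve spontaneously, gives a course of 7 to 10 days, and reads efficacy at Day 8. A rule met by any reduction, or by either remission alone, credits recovery that would have occurred on any product. In a non-inferiority comparison, anything that pulls the arms together favours the claim. It also blurs the comparison of the three posologies.

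Entry without a positive culture adds to this. Section 15.2 excludes suspected viral cases and the elimination criteria remove other diagnoses, but neither reliably catches a viral case taken for bacterial. Of viral cases, the introduction says "it is estimated that 50% of these will be misdiagnosed as bacterial". No rule says how a culture-negative eye is scored.

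**Working it through.** **1. The plan's sample size.** The inputs are unweighted means of the rates tabulated in section 23.
- Absolute eradication on drug: (74.53 + 76.92 + 57.96)/3 = 69.80%. On vehicle: (56.03 + 58.33 + 45.54)/3 = 53.30%.
- Specific eradication on drug: (98.51 + 86.36 + 94.12 + 92.31 + 90.39)/5 = 92.34%. On vehicle: (59.62 + 50.00 + 80.00 + 70.83 + 70.15)/5 = 66.12%.

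The Fleiss formula of Annex 1 (two-sided 5%, 80% power, 1:1, continuity corrected) reproduces the stated 147 and 44 per group. Both are sizes for drug versus placebo on disappearance of bacteria. They correspond to a microbiological endpoint, not to the and/or or either-remission rule, and they are not non-inferiority sizes.

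**2. Can the rules disagree?** Take 60 units per arm (the plan's 60 eyes; the tables say subjects). The 95% culture threshold then needs at least 0.95 × 60 = 57 clear cultures. With X binomial(60, p):

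| True eradication p | P(X ≥ 57) |
|---|---|
| 69.8% | 1.3e-6 |
| 92.34% | 32% |
| 95% | 65% |

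An arm performing exactly as the sample-size section expects would probably fail this threshold, while its patients could still succeed under the and/or rule.

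**3. Can remission be scored for a patient?** The closing rule needs a yes or no for each patient. The culture entry and four of the five sign entries are proportions of a group. The fifth, corneal defects, can be applied to one eye, but any affected area below 95% passes. No patient-level definition of remission follows from these entries.

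**4. Direction of the narrowing (illustration only).** Assume that clinical remission s is equal in both arms and independent of culture. Either-remission success is 1 − (1 − p)(1 − s), so a culture gap g becomes (1 − s)g. The documents give no clinical remission rate; s = 50% to 90% is assumed.
- Absolute gap: 69.8 − 53.3 = 16.5 points, which becomes 8.3 to 1.7.
- Specific gap: 92.34 − 66.12 = 26.2 points, which becomes 13.1 to 2.6.
- With a culture-positive share c as well, the gap is c(1 − s)g. One cited study recruited 1180 patients and tabulates 424 + 423 = 847, so c = 847/1180 = 72% as a proxy. The documents do not say why 333 are absent. The 26.2 points then become 9.4 to 1.9.
- If clinical remission itself favours drug by 10 to 16.5 points (vehicle rate 50% to 80%), the 16.5-point gap becomes 6.3 to 13.2. The narrowing is smaller but in the same direction.

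**5. Precision of an eradication endpoint.** Exact binomial enumeration, equal arms, non-inferiority declared if the lower 95% Newcombe limit lies above an assumed −15 points. The 43 evaluable is 60 × 0.718.

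| Eradication in both arms | 60 per arm | 43 per arm |
|---|---|---|
| 92.34% | 81% | 65% |
| 69.8% | 45% | 35% |

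**The case against.** The strongest defence is that the plan does label a criterion. The and/or rule stands under Main efficacy criterion in both places, so a reader who infers that nothing is named as primary goes further than the text. This stands. The defect is that the labelled criterion is a loose composite, contradicted by the culture sentence above it and by the later rules.

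A reader might also count three rival rules. The tables and the closing list can instead be read as one chain, in which the tables describe remission and the list uses it. That reading is fair, but it does not rescue the chain, because remission described by group percentages cannot be applied to a patient. Nor do the tables require every sign to be absent in 95%; of the five signs, only secretion, chemosis and eyelid edema carry that text. Similar wording in the safety tables suggests a general acceptance target. If so, the plan should say that it is not a success rule.

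Finally, it is tempting to say that only the lenient rules credit natural recovery, or to quote a probability of false non-inferiority. The documents support neither. Section 8 lists no vehicle arm, so every endpoint credits recovery to some degree; vehicle eradication itself averaged 53.3% and 66.12%. No margin, clinical remission rate or culture-positive share is given for this trial, and the cited rates come largely from three-day studies.

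**Conclusion.** The point holds as a conflict in the text and must be fixed. The labelled main criterion can be met by any reduction in flora or signs, the same section contradicts it, and the remission rule cannot be scored for a patient. That the rules can disagree rests on the plan's own eradication rates and on taking 60 units per arm.

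The expected narrowing of differences, which is anti-conservative for non-inferiority, is supported in direction by the protocol's account of spontaneous resolution, the Day 8 reading and entry without a positive culture. Its size is not established. The ranges above depend on assumed clinical rates, independence and, in one case, a proxy share, and they concern drug versus vehicle rather than active versus active.

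**What to change.** In section 7.1 and the synopsis:
- Replace the and/or rule and the either-remission rule with one primary responder definition at Day 8. Score it per patient, or per eye with allowance for two eyes from one patient.
- Consider bacterial eradication among randomised patients with a positive baseline culture. This is the option consistent with the type of endpoint in section 23. That section offers both absolute and organism-specific eradication, so state which is meant and how this set relates to ITT and PP.
- Report clinical remission as a separate endpoint in all treated patients, defined per patient on one fixed list of signs. Section 6.2 names signs as well as culture.
- Remove the 95% group thresholds as success criteria, or reconcile them with the primary rule.
- State how culture-negative eyes are handled, and give the expected culture-positive number as an assumption. Do not use 44 as a target, because it is a superiority-over-placebo size.

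Cultures and signs are already collected at baseline and Day 8, so no procedure changes. The cost is fewer evaluable eyes and the lower power shown above, which the plan should state openly. The fix reduces the natural-recovery problem without removing it. If a vehicle-like product cleared 85% by Day 8 (assumed) against 92.34%, it would still be declared non-inferior 25% of the time at 60 per arm and 15 points.

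### The main efficacy criterion compares five groups for culture and an undivided study medication for signs, while the hypothesis needs each PRO-157 posology against both comparators; no primary contrast is named

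*Combined protocol and SAP*

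**What the plan says.** The relevant statements are these.

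- **Main efficacy criterion, culture (section 7.1).** A reduction in number or species of bacteria is judged by "comparing the basal culture against the end between the five different groups of patients". The synopsis has almost the same words, "comparing the basal culture against the final between the five different groups of patients", and its criterion contains no phrase naming a comparator.
- **Main efficacy criterion, signs and symptoms (section 7.1).** The same sentence, after an and/or, ends "when comparing the study medication versus Moxifloxacin and versus Gatifloxacin from baseline to final visit". The posologies are not listed separately.
- **Effectiveness rule (section 7.1).** After the tables of signs and culture come the words "The drugs under study will be considered effective if the patient has any of the following", followed by clinical remission, microbiological remission or both. This is a rule for one patient. The tables add thresholds, mostly absence in 95% of subjects. Neither is a comparison between arms.
- **Hypothesis (section 6.1).** Under Ha, PRO-157 "is so safe and effective in some of its different posologies when demonstrating non-inferiority when compared against Moxifloxacin and Gatifloxacin".
- **Objectives (section 6.2).** Safety and efficacy are to be evaluated "in three different posologies versus Moxifloxacin and versus Gatifloxacin in patients with bacterial conjunctivitis".
- **Size (synopsis).** "Number of participants: 300 eyes, 60 eyes per treatment group".
- **Statistics (section 23).** The sample size rests on a two-group difference between drug and placebo. The only analysis named is a bivariate one in the per-protocol set, with no test, contrast, margin or multiplicity rule.

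**The concern.** Three posologies and two comparators give 3 × 2 = 6 contrasts that bear on Ha. Five groups taken together give 10 pairs. The other four (three between posologies, one between moxifloxacin and gatifloxacin) say nothing about PRO-157 against a comparator. An overall comparison mixes all ten and does not show which posology is as good as the marketed drugs, which is the question a phase II trial of three posologies should answer.

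A non-significant overall result could be taken as showing that all arms are alike when a posology is no better than vehicle. A significant one could be held against PRO-157 when two of its posologies do well. With no contrast named in advance, the analyst could choose among several after seeing the data.

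**Working it through.** **The plan's own sample size.** Annex 1 uses the Fleiss formula with P1 = 0.698, P2 = 0.533, two-sided α = 0.05 and power 80%. It gives m′ = 135.272. The continuity correction is m = 0.25 m′ [1 + √(1 + 4/(m′ × 0.165))]² = 147.1, stated as 147 (148 if rounded up). For 0.9234 against 0.6612 it gives 44, as stated. Both figures reproduce. They size a drug-versus-placebo difference, which is neither a five-group comparison nor non-inferiority to an active drug, so the sample size does not show which contrast was meant.

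**If the five-group wording means an overall test.** Assumptions: Pearson chi-square on 4 df at 0.05, 60 independent eyes per arm, and the rates averaged from Cuadro 1 (69.8% on drug, 53.3% on vehicle). The non-centrality is λ = 60 × Σ(p_j − p̄)² / [p̄(1 − p̄)].

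- One posology at 0.533 and four arms at 0.698: p̄ = 0.665 and λ = 60 × 0.02178 / 0.22278 = 5.87. Power is about 46% by this approximation and 45% by simulation, so the weak posology is missed about 55% of the time.
- All three posologies at 0.533 and both comparators at 0.698: p̄ = 0.599 and λ = 60 × 0.03267 / 0.24020 = 8.16. Power is about 62%, so the failure is missed about 38% of the time.
- All arms equal: simulated rejection 5%, as it should be.

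**Can the overall and pairwise answers disagree?** The documents give no margin, so 10, 15 and 20 points are assumed. The lower limit is d − 1.96 √[p₁(1 − p₁)/60 + p₂(1 − p₂)/60], where d is PRO-157 minus comparator.

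| Successes out of 60 (three posologies; two comparators) | Overall chi-square | Lower limits, by posology (same against both comparators) |
|---|---|---|
| 37, 38, 38; 42, 42 | 23.2 / 13.53 = 1.72, p = 0.79 | −25.2, −23.5, −23.5 points |
| 57, 56, 45; 55, 55 | 95.2 / 5.72 = 16.65, p = 0.002 | −5.6, −7.8, −29.7 points |

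In the first row the overall test sees no difference, yet no posology is non-inferior at any of the three margins. In the second it is clearly significant, yet two posologies are non-inferior to both comparators at 10 points.

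In simulation with all five true rates at 69.8%, a non-significant overall test went with no posology non-inferior to both comparators in 70%, 42% and 16% of trials at margins of 10, 15 and 20 points. With all three posologies truly 15 points worse, the overall test was non-significant in about 47% of trials.

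**If the study medication were taken as one group.** One posology at 53.3% and two at 69.8% average (53.3 + 2 × 69.8)/3 = 64.3%, which would partly hide the weak one.

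**The case against.** The strongest reply is that the plan names no overall test. Naming five groups may only list the arms, the closing comparator clause in section 7.1 may govern the culture part too, and section 6.2 lists culture among the means of evaluating three posologies against each comparator. The only named analysis is bivariate. On that reading the intended contrasts are pairwise and the chi-square figures describe a test nobody planned.

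Much of this stands. The chi-square is our assumption, and the figures show only what follows if the wording is taken literally. The reply does not remove the ambiguity: the synopsis criterion has the five-group wording alone, and no text makes the pairwise contrasts primary.

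A reader might infer more from the text in four ways that it does not support:

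- **That the five-group comparison decides the trial.** The criterion is an and/or sentence followed by a per-patient rule and thresholds. Nothing gives the five-group comparison that standing.
- **That the posologies will be pooled.** This is one reading of the undivided study medication. No section says so, and the hypothesis and objectives distinguish three posologies.
- **That every posology must succeed.** Ha asks only for some.
- **That an overall test would often raise a false alarm because the two comparators differ.** Section 23 names Zymar as the gatifloxacin product. With gatifloxacin at its Cuadro 1 rate of 76.92% and the other four arms at 74.53%, rejection is about 6%, close to nominal. The lower gatifloxacin rate in that table belongs to Zymaxid.

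**Conclusion.** The point holds as a mismatch between the criterion and the hypothesis. The plan states contrasts, but none is clearly the posology-by-comparator contrast that Ha requires, and none is primary. Taken literally as an overall test, the culture wording would miss one vehicle-like posology about 55% of the time and three about 38% of the time, and it could contradict the pairwise answer in either direction. These sizes rest on the assumed chi-square, independent eyes, 60 per arm and the plan's averaged rates. The non-inferiority illustrations also rest on assumed margins and Wald intervals. That the contrasts differ follows from the text alone. The change should be made, though nothing here shows that the sponsor intended an overall test.

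**What to change.** In the synopsis and section 7.1, replace both the five-group wording and the undivided study-medication wording. For each PRO-157 posology separately, specify the difference in success proportion against moxifloxacin and against gatifloxacin, with its confidence interval, judged against a prespecified and justified non-inferiority margin. Then state that:

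1. a posology succeeds only if it is non-inferior to both comparators;
2. Ha is met if at least one posology succeeds, with a multiplicity adjustment across the three posologies (three independent tests at one-sided 0.025 would give 1 − 0.975³ = 7.3%);
3. any five-group, posology-posology or moxifloxacin-gatifloxacin comparison is descriptive.

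Say also which of the existing effectiveness rules defines a success; otherwise the per-patient rule and the 95% thresholds still compete with the new contrast. Intervals without a margin and these rules could not conclude non-inferiority.

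The cost is wording, six intervals to report, and descriptive status for any overall comparison. The change needs no new visits or procedures, but it does not settle whether 60 eyes per arm is enough. With equal true rates of 69.8% and one-sided 0.025, power for a single contrast is 22%, 43% and 67% at assumed margins of 10, 15 and 20 points. At 92.34% it is 54%, 87% and 98%. That should be weighed when the margin is set.
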